5.6 Duration of Follow Up

Patients will be followed for up to 52 weeks (1 year) after removal from study or until death, whichever occurs first. Patients removed from study for unacceptable adverse event(s) will be followed until resolution or stabilization of the adverse event. Patients will be followed every 3 months by phone after removal from study.

6. DOSING DELAYS/DOSE MODIFICATIONS

Summary of dose delays and modifications allowed on study (please see sections below for detail):

- Dose delay or modification of decitabine is allowed for patients diagnosed with MDS (per institutional guidelines) as described in [section 6.1](#). If a patient with MDS is in a CR, due for both decitabine and ipilimumab and a dose delay of decitabine is recommended, then decitabine and ipilimumab can be delayed so that they can be dosed together.
- Dose delay or modification of decitabine is allowed for patients diagnosed with AML in absence of disease if there are severe cytopenias after discussion with overall PI. Please see pre-dose requirements in section 5.1.
- Holding ipilimumab is allowed based on recommendations in section 6.2.
- If ipilimumab is held per recommendations in section 6.2, decitabine can continue alone. Ipilimumab may be re-introduced upon ipilimumab-AE resolution after discussion with overall PI. Delayed benefit from checkpoint blockade may occur.
- Participants may delay ipilimumab dosing beyond 8 weeks after discussion and approval by the overall PI (each clinical situation will be reviewed on case by case basis).
- Missed doses of ipilimumab are not given later.

6.1 Dose Delay Recommendations for Patients with Suspected Decitabine Related Toxicity

If the toxicity is thought to be due to decitabine:

If toxicity is thought to be due to decitabine alone, then ipilimumab dosing can be continued as monotherapy. This decision should be made with the overall PI.

- **AML:** Dose modification is not recommended for patients with AML. For cycle 4 onward, if there is evidence of marrow hypocellularity with <5% blasts, then can consider delaying treatment cycle for up to 14 days, in absence of disease.
- **MDS:** Dose delay can be considered (not mandatory) in patients with MDS per FDA package label after evidence of marrow remission or better. Any other treatment delays must be discussed with the Overall PI.

Patients that have grade 3 or higher thrombocytopenia (50,000/mm³ or less) OR grade 3 or higher neutropenia (1000/mm³ or less) at the time of screening are not recommended for dose reduction until after response evaluation at the end of cycle 2. If there is evidence of marrow remission or better for patients with MDS on study, then dose delay may be considered for subsequent cycles per institutional guidelines. If there is evidence of persistent disease, then would not recommend delaying treatment unless thought to be

due to decitabine (and not disease).

6.2 Dose Delay Recommendations for Patients with Suspected Ipilimumab Toxicity or Combination Therapy

Intra-patient dose modification (reductions or increases) of ipilimumab is not allowed in this study.

Decisions to delay an ipilimumab dose must be made on specified safety criteria. Treatment with ipilimumab will be delayed or discontinued if the subject experiences at least one adverse event, specified below, considered by the investigator to be **“possibly,” “probably,” or “definitely” related to ipilimumab treatment.**

Any adverse event that will prompt a delayed dose or discontinuation of ipilimumab must be reported. All AEs that require dose holding (for ipilimumab) will be reviewed during regularly scheduled conference call with the PI and co-investigators. Calls will be planned at a minimum of every 4-6 weeks. A representative from the site (co-investigator, research nurse, or clinical trial coordinator) will be required to be present on the call. **The investigator should contact the study PI or drug monitor to discuss any questions that may arise.**

Doses of ipilimumab will be referred to as dose #1, dose #2, dose #3, or dose #4 during the induction phase and dose #5, dose #6, dose #7 or dose #8 during the maintenance phase. The induction phase will include the first four doses of ipilimumab and the maintenance phase will include the last four doses of ipilimumab. If there are any ipilimumab dose delays, the cycle and day will not change. The “study cycle” number is determined by the cycle of decitabine that the patient is on (with “cycle 1” starting as the first cycle of COMBINATION with ipilimumab; the priming phase of decitabine monotherapy could be considered “cycle 0” for purposes of this study). If there is a delay in ipilimumab dosing, decitabine may be continued as scheduled. Disease response assessments will be as scheduled regardless of how many doses of ipilimumab is administered. As an example, if dose #2 of ipilimumab (which would be due on cycle 2 day 1) is delayed for four weeks due to an ipilimumab related toxicity, decitabine can still be administered on cycle 2 days 1-5 and the scheduled disease response assessment will still occur at the end of cycle 2. If the ipilimumab related toxicity has resolved by cycle 3 day 1, then dose #2 of ipilimumab will be given then concurrent with decitabine. Continuing decitabine will help to maintain disease control given the proliferative nature of AML. We will capture how many doses of ipilimumab that patients are able to receive in this study.

Delay window: If ipilimumab dosing must be delayed for > 4 weeks +/- 3 days for holiday or scheduling logistics (more than 8 weeks [+/- 3 days] since the prior dose administration), then patients must come off treatment. For example, if patient cannot receive ipilimumab on cycle 2 day 1 due to development of grade 2 colitis, then the patient’s dose will be delayed to cycle 3 day 1. If the patient cannot be dosed on cycle 3 day 1 (and it has now been more than 8 weeks since last dose), then the patient must come off treatment.

Exceptions may be made to hold ipilimumab for > 8 weeks after discussion with overall PI for grade 2 or lower ipi-induced immune related AEs and GVHD events that are less than grade III.

Patients may remain on decitabine alone until ipilimumab can be re-introduced if patients demonstrate continued benefit and resolution of suspected ipilimumab-induced AE to grade 1 or baseline (skin GVHD can be controlled with topical steroids).

Suspicion for graft versus host disease (GVHD): If there is a concern for GVHD, then we recommend consideration of a biopsy for diagnostic work-up if clinically appropriate. Evidence of grade III or higher acute GVHD would be considered a DLT (except for skin GVHD, must have at least stage 3 involvement to be a DLT) as this often triggers systemic corticosteroids. These patients would stop receiving study treatment (both ipilimumab and decitabine), and followed for up to 1 year after treatment for AE resolution, response and survival. Those with skin GVHD that is overall grade II with stage 1-2 involvement or less will be able to stay on study. Topical corticosteroids are allowed. For GVHD events that are less than grade III, ipilimumab dose can be skipped (decitabine can continue) until event resolution or when the event is controlled without requiring systemic corticosteroids or immunosuppressive agents (exception: topical steroids) (missed ipilimumab doses will not be made up); these patients may remain on study. Please see [Appendix B](#) for resources to be used for acute and chronic GVHD grading.

It is necessary to delay ipilimumab dosing for the following related adverse events:

- Any \geq Grade 2 non-skin related adverse event (including immune related AE (irAEs)), except for asymptomatic laboratory abnormalities, grade 2-3 fatigue, and grade 2 anorexia (as the latter two events can be caused by disease alone). Treatment does not need to be delayed for controlled (on treatment) or recently treated infections.
- Any \geq Grade 3 non-hematologic laboratory abnormality except for grade 3 fatigue (as can be caused by disease). Treatment does not need to be delayed for controlled (on treatment) or recently treated infections.
- Any adverse event, laboratory abnormality or intercurrent illness that, in the judgment of the investigator, presents a substantial clinical risk to the subject with continued dosing
- Any \geq Grade 3 skin related adverse event (unless considered to be related to underlying disease, leukemia cutis, or a drug-allergy that is not due to study drug (ie antibiotics))
- An event that is not considered to be necessarily related to ipilimumab but requires a brief course of corticosteroid therapy.
 - An example, if a patient develops Sweet's syndrome (febrile neutrophilic dermatosis, confirmed by skin biopsy), then prednisone would be warranted. Patients would be allowed to continue decitabine to maintain disease control.
- An event that is considered to be due to ipilimumab, such as immune related AEs that are grade 2 or less can receive corticosteroids if deemed clinically necessary so as long as they are tapered off by next dose. If ipilimumab dosing must be delayed for > 4 weeks ($+/ - 3$ days for holiday or scheduling logistics) (more than 8 weeks since the prior dose administration) for any of the above reasons, patients must come off treatment.
- Decitabine may continue if AE considered to be due to ipilimumab

If there is a dose delay in ipilimumab:

For any dose delay, patients must re-meet laboratory criteria (including complete blood count with differential and platelets, comprehensive metabolic profile including liver enzymes) to be treated again on day of therapy (prior to dosing).

Resuming ipilimumab:

- Should coincide with day 1 of treatment cycle.
- If the adverse event is suspected to be due to ipilimumab, then the AE must resolve to \leq grade 1 severity or returns to baseline within 4 weeks of initiating the dose delay (no more than 8 weeks since the most recent prior dose administration). This includes immune-related AE. Patients must be tapered off prednisone prior to resuming ipilimumab.
- If the *adverse event has resolved to \leq grade 1*, ipilimumab dosing may be restarted at the next scheduled time point per protocol. Please see suggested guidelines for management of specific immune related adverse events (see [Appendix C](#)). Please note that re-initiating treatment may be associated with recurrence or exacerbation of autoimmune or inflammatory events. In some instances clinical resolution of events such as colitis may be associated with residual pathologic changes and should require evaluation of complete resolution prior to restarting therapy.
- If ipilimumab dosing must be delayed for > 4 weeks ($+/- 3$ days for holiday or scheduling logistics) (more than 8 weeks [$+/- 3$ days] since the prior dose administration) for any of the above reasons, patients must come off treatment.
- Autoimmune/inflammatory events are presumably related to the mechanisms of action of ipilimumab and potentially to a therapeutic effect. The incidence and severity of these events may be dose related, but once initiated, there is no evidence that lowered doses can be administered without continued autoimmune activity and there has so far been no demonstrable benefit to continuing ipilimumab after an autoimmune event during the initial treatment. The significance and benefit of toxicity or continued treatment in the maintenance phase has not been determined. Typically no dose modification is used for ipilimumab.

Permanent Discontinuation of Ipilimumab for Related Adverse Events

If discontinuing ipilimumab, participants will have the option to continue decitabine alone on study if they are determined to be clinically benefitting from treatment at the investigator's discretion.

Permanently discontinue ipilimumab for any of the following:

- Grade III or higher acute GVHD.
- Persistent adverse reactions that requires holding more than 2 ipilimumab doses (exception: patients with a GVH event(s) that is determined to be less than a grade III who are benefitting from study treatment can continue on study after approval from overall PI).
- Any persistent grade 3 or 4 event (see exceptions below in [section 6.2.1](#)).
- Any immune related AE that is grade 3 or higher requiring systemic corticosteroids at a dose of 1 to 2 mg/kg/day of prednisone or equivalent. Immune related AEs that were

grade 2 or less are allowed to stay on study and receive corticosteroids if necessary so as long as they are tapered off by next scheduled dose of ipilimumab. They cannot be delayed by more than 4 weeks (meaning 8 weeks between doses), or they have to come off study.

- Severe or life-threatening adverse reactions, including any of the following:
 - Colitis with abdominal pain, fever, ileus, or peritoneal signs; increase in stool frequency (7 or more over baseline), stool incontinence, need for IV hydration for more than 24 hours, gastrointestinal hemorrhage, and gastrointestinal perforation
 - Aspartate aminotransferase (AST) or alanine aminotransferase (ALT) >5 times the upper limit of normal or total bilirubin >3 times the upper limit of normal
 - Stevens-Johnson syndrome, toxic epidermal necrolysis, or rash complicated by full thickness dermal ulceration, or necrotic, bullous, or hemorrhagic manifestations
 - Severe motor or sensory neuropathy, Guillain-Barré syndrome, or myasthenia gravis
 - Severe immune-mediated reactions involving any organ system (e.g., nephritis, pneumonitis, pancreatitis, non-infectious myocarditis)
 - Immune-mediated ocular disease that is unresponsive to topical immunosuppressive therapy
 - Any adverse event, laboratory abnormality or intercurrent illness which, in the judgment of the investigator, presents organ specific injury and/or a substantial clinical risk to the patient with continued dosing.

The following neurological adverse event requires permanent discontinuation of ipilimumab and defines unacceptable neurotoxicity:

- Any motor neurologic toxicity >/= grade 3 regardless of causality
- Any >/= grade 3 treatment related sensory neurologic toxicity

Please refer to [Appendix C](#) and the Investigator Brochure for suggested specific treatment algorithms.

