- **Priming Phase** (Lead- In): The priming phase includes decitabine alone at 20 mg/m² given daily for 5 consecutive doses starting on days 1-5 on a 28 day cycle to provide priming and disease control. Hypomethylating agents, such as decitabine have been tested in the post allo-HCT setting with evidence of safety and tolerability [57-59] including at the same dose proposed in this study.
- **Induction Phase** (cycles 1-4): Cycles 1 through 4 will include treatment with decitabine 20 mg/m² daily for five consecutive doses on days 1-5 plus ipilimumab (given per dose level) on day 1 on a 28 day cycle. There will be three dose escalation levels tested: 3.0 mg/kg (starting dose), 5.0 mg/kg, and 10.0 mg/kg. There will be a dose de-escalation level provided (1.0 mg/kg). Pharmacokinetic data generated from the initial pilot study demonstrated that higher doses of ipilimumab correlated with increased ipilimumab exposure and that those doses may be sufficient to saturate CTLA-4 binding sites [5]. The starting dose level of 3.0 mg/kg was tested in the phase 1b study for relapsed hematologic malignancies after allo-HCT with demonstration of safety and tolerability [4]. There was evidence of preliminary clinical activity (discussed in Section 2.4 in detail) in this study at 10 mg/kg but with evidence of immune related adverse events and GVHD in some cases. Thus we will also test the dose of 5.0 mg/kg.
- **Maintenance Phase** (cycles 5-12): Cycles 5 through 12 will include treatment with decitabine 20 mg/m² daily for five consecutive doses on days 1-5 on a 28 day cycle. Ipilimumab will continue on day 1 every 8 weeks for a total of 4 doses.

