Management and dose delays associated with the above adverse events are outlined in [Section 6](#).

Dose escalation will proceed within each cohort according to the following scheme. Dose-limiting toxicity (DLT) is defined above.

For patients who are removed from treatment because of a > 4 week delay in receiving the next dose of ipilimumab: this will be classified as a DLT only if AE resulting in the treatment delay qualifies as a DLT.

Number of Patients with DLT at a Given Dose Level	Escalation Decision Rule
0 out of 3	Enter 3 patients at the next dose level.
1 out of 3	Enter at least 3 more patients at this dose level. 
 • If 0 of these 3 patients experience DLT, proceed to the next dose level. • If 1 or more of this group experience DLT, then dose escalation is stopped, and this dose is declared the maximally administered dose. Three (3) additional patients will be entered at the next lowest dose level if only 3 patients were treated previously at that dose.
≥ 2	Dose escalation will be stopped. This dose level will be declared the maximally administered dose (highest dose administered). Three (3) additional patients will be entered at the next lowest dose level if only 3 patients were treated previously at that dose.
≤ 1 out of 6 at highest dose level below the maximally administered dose	This is generally the recommended phase 2 dose. At least 6 patients must be entered at the recommended phase 2 dose.

Delayed toxicities (toxicities after 8 weeks of combination therapy): As delayed toxicity may occur (immune related AE) at any point after checkpoint blockade therapy, we recommend that any event beyond the first 8 weeks of combination therapy that is considered to be an immune related AE or concerning for GVHD be reported to the Overall PI. These events will be captured and reported, but will not determine dose-escalation. These patients would also be removed from study if they have a toxicity event described in [section 5.2](#).

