- n: For those with known HIV they must get a CD4 count and an HIV viral load (PCR).
- o: Baseline echocardiogram and EKG required for screening (if done within 4 weeks of treatment start does not need to repeat unless there is a clinical concern) and at any other time that is clinically indicated during the trial as it relates to footnote q
- p: Peripheral blood, aspirate, core biopsy, or FFPE to be collected per schedule described correlative table below.
- q: Alert PI if there is concern for cardiac toxicity (minimum assessment: cardiology consult, EKG, echocardiogram, and labs CPK and troponin; refer to section 6.4.7)
- r: Please see section 7.3.5 of the protocol for reporting requirements for GVHD and suspected immune related AEs to enable central review
- s: MUGA scan is a suitable alternative to an echocardiogram
- t: For participants enrolled on Arm A (post transplant), a formal GVHD assessment is required at minimum on Day 1 of each cycle utilizing the GVHD assessment worksheet provided in Appendix B

	Maintenance cycles and end of study										
	C5 D1 ^b	C6 D1 ^b	C7 D1 ^b	C7 D24 ^a	C8 D1 ^b	C9 D1 ^b	C10 D1 ^b	C10 D24 ^a	C11 D1 ^b	C12 D1 ^b	End of study ^{i,j}
Ipilimumab^A	X		X			X			X		
Decitabine^B	X	X	X		X	X	X		X	X	
Concurrent meds	X	X	X		X	X	X		X	X	
Physical Exam	X	X	X		X	X	X		X	X	X ^k
Vital signs	X	X	X		X	X	X		X	X	
Height	X										
Weight	X	X	X		X	X	X		X	X	
Performance status	X	X	X		X	X	X		X	X	
CBC w/diff, plts	X	X	X	X	X	X	X	X	X	X	X
Serum chemistry^c	X	X	X		X	X	X		X	X	X
Immune-related labs^d			X				X				X
Adverse event evaluation^{e,f,m}	X	X	X		X	X	X		X	X	X ^k
GVHD Assessment	X	X	X		X	X	X		X	X	X
Bone marrow^f				X ^f				X			X ^f
T cell chimerism^g											X
Correlative studies^h				X				X			X

A: Ipilimumab: Dose as assigned by dose level. Administered every 8 weeks. Dosed per weight on day 1 of a cycle.
B: Decitabine: 20 mg/m² daily IV for 5 consecutive days on days 1-5. Dosed per weight on day 1 of the lead in
a: Can be done any time between day 24-28
b: +/- 3 days
c: Albumin, alkaline phosphatase, total bilirubin, bicarbonate, BUN, calcium, chloride, creatinine, glucose, potassium, total protein, SGOT [AST], SGPT [ALT], sodium, uric acid, magnesium, phosphorus.
d: At baseline, C1D1, and then every 3 cycles thereafter or more frequently when clinically indicated: gamma-GT, direct bilirubin, LDH, TSH, and lipase
e: Please see [Appendix F](#) for helpful study check list including immune related AE evaluation

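### Section 6.2 equates an ipilimumab delay of over 4 weeks with over 8 weeks since the last dose; this fails for 8-weekly maintenance doses, where an on-time dose is already at 8 weeks

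*Combined protocol and SAP*

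**What the plan says.** Section 6.2 (Delay window) sets the limit as a delay of more than 4 weeks, with 3 days for holidays or scheduling, and glosses it as "more than 8 weeks [+/- 3 days] since the prior dose administration), then patients must come off treatment". The same pairing appears at four more places in 6.2:

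- at the end of the list of events that require a hold: "more than 8 weeks since the prior dose administration) for any of the above reasons, patients must come off treatment";
- in the rule for resuming, where the event must settle "within 4 weeks of initiating the dose delay (no more than 8 weeks since the most recent prior dose administration";
- in the later bullet under resuming that repeats the off-treatment rule;
- under permanent discontinuation: "They cannot be delayed by more than 4 weeks (meaning 8 weeks between doses), or they have to come off study".

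The day of resumption is also fixed: "Should coincide with day 1 of treatment cycle".

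Nothing confines these statements to induction. Section 6.2 numbers doses 5 to 8 as the maintenance doses, but its worked examples use only cycles 2 and 3.

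On schedule, Section 5.1 gives ipilimumab every 4 weeks in induction. For maintenance, Section 2.3 says "Ipilimumab will continue on day 1 every 8 weeks for a total of 4 doses". The maintenance calendar in Section 10.1 marks cycles 5, 7, 9 and 11, with the footnote "Dose as assigned by dose level. Administered every 8 weeks. Dosed per weight on day 1 of a cycle". Section 5.1 also allows further maintenance, with ipilimumab every other cycle, for patients who are benefitting.

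**The concern.** The bracketed gloss works only if the next dose was due 4 weeks after the last. In 8-weekly maintenance the planned gap is already 8 weeks, so the two halves of one rule set different limits.

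The patients affected entered maintenance with stable disease or better (Section 5.1). Section 6.2 makes a hold mandatory for most related non-skin events of grade 2 or above, and it intends patients with grade 2 immune events to resume once these settle to grade 1 or less. If such a hold falls at cycle 7, 9 or 11 and the event settles within one cycle, the delay wording permits dosing on the next day 1. The interval wording takes the patient off treatment (off study, in the permanent-discontinuation bullet). What is at stake is whether the patient receives the remaining ipilimumab doses, and whether the same situation is always handled in the same way.

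**Working it through.** **Inputs.** The cycle length is 28 days (Section 5.1). Ipilimumab is due on day 1 of cycles 1, 2, 3, 4, 5, 7, 9 and 11 (Section 10.1). The delay limit is 28 days, or 31 with the 3-day allowance. The interval limit is 56 days, or 59 with the allowance (both Section 6.2).

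**Formula.** Days since prior dose = planned interval + delay. The room left by the interval form is 56 (or 59) minus the planned interval.

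**The plan's own equivalence first.** For a dose due at 4 weeks, 28 + 28 = 56 days = 8 weeks. This matches the 6.2 example in which dose 2 moves from cycle 2 to cycle 3. It also holds at cycle 5, which falls 28 days after cycle 4.

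| Dose due at | Planned interval | Delay allowed, interval form | Delay allowed, delay form | Latest day, delay form |
|---|---|---|---|---|
| C2, C3, C4, C5 | 28 | 56 − 28 = 28 (31) | 28 (31) | 28 + 28 = 56 (59) |
| C7, C9, C11 | 56 | 56 − 56 = 0 (3) | 28 (31) | 56 + 28 = 84 (87) |

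Figures are days; those in brackets include the 3-day allowance. In maintenance the limits differ by 84 − 56 = 28 days, for 3 of the 8 planned doses and every dose in extended maintenance.

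**One-cycle hold.** Resumption falls on day 1 of a cycle, so the earliest day after a held cycle 7 dose is cycle 8 day 1: 56 + 28 = 84. The delay is exactly 28 days, which is not more than 4 weeks. The interval is 84 − 59 = 25 days over the interval limit, even with the allowance.

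**Resume rule.** Counted from the scheduled date, the event has 28 days to settle by the first half of the rule and 56 − 56 = 0 days by the second. An event that starts and settles before the due date causes no hold, so the 0 applies only once a dose has actually been held.

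**DLT window.** Cycle 7 day 1 is 6 × 28 = 168 days after cycle 1 day 1, well past the 56-day window. Section 5.2 also counts removal for delay as a DLT only if the event itself qualifies.

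**The case against.** The strongest reply is that the overall PI already controls this. The Section 6 summary requires discussion with the PI before ipilimumab is re-introduced. Section 6.2 puts every ipilimumab hold on calls held at least every 4 to 6 weeks. Section 6 lets the PI approve delays past 8 weeks case by case, and 6.2 has its own exception for immune events of grade 2 or lower and GVHD below grade III. Higher-grade immune events generally end ipilimumab anyway, so most patients who could resume fall within the exceptions. Section 6.2 also lets a patient who is benefitting continue decitabine alone. All of this stands, and it greatly weakens any claim that sites would diverge on their own readings. It does not repair the rule. The exceptions are discretionary, they use the same 8-week figure, and they do not say whether a one-cycle maintenance hold needs one.

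A second reply is that day 84 is not the resumption day. The Section 6 summary says missed doses are not made up, and 6.2 speaks of restarting at the next scheduled time. On that reading a held cycle 7 dose waits until cycle 9, at 56 + 56 = 112 days. The delay is then 56 days and both forms remove the patient. However, the 6.2 example gives a delayed dose on the next cycle's day 1. The text supports both readings, so the fix must settle this too.

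A third reply is that a stricter maintenance limit may be deliberate. No text says so, but none rules it out. A reader might infer that the delay form is intended because Section 5.2 uses it alone: "For patients who are removed from treatment because of a > 4 week delay in receiving the next dose of ipilimumab". That sentence sits in the DLT section, whose window covers only 4-weekly dosing, where the two forms agree. It says little about maintenance.

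**Conclusion.** The point holds as an internal conflict in a stated rule. The two forms agree for cycles 2 to 5 and differ by 28 days for every 8-weekly dose. Read literally, the interval form makes a one-cycle maintenance hold a removal unless an exception is granted. This rests on 28-day cycles, resumption on day 1 of a cycle, and a held dose being allowed at the next cycle, as in the 6.2 example.

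Four stronger inferences are not supported:

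- That an on-time maintenance dose breaches the limit. It sits at 8 weeks, and the rule says more than 8 weeks.
- That DLT assessment, escalation or the RP2D is affected. These doses fall outside the window, and Section 5.2 says later toxicities do not determine escalation.
- That sites will give materially different exposure. PI oversight makes this unlikely, and the documents give no figure for how many patients will have a maintenance hold.
- That 12 weeks is plainly what the sponsor meant. It follows from adding the stated 4 weeks to the stated 8, but the intent for maintenance is not written down.

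Severity: minor to moderate rule correction.

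**What to change.** At the five places in Section 6.2, define the limit as more than 4 weeks (+/- 3 days) past the scheduled ipilimumab date. Spell this out as more than 8 weeks since the prior dose for 4-weekly doses (cycles 2 to 5) and more than 12 weeks for every 8-weekly maintenance dose, including extended maintenance. In the Section 6 summary bullet on PI approval and in the 6.2 exceptions sentence, replace the 8-week figure with a reference to this limit.

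State that a held maintenance dose may be given on day 1 of the next cycle, as in the 6.2 example. Reconcile the Section 6 bullet on missed doses and the 6.2 sentence on restarting at the next scheduled time with that statement.

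The sponsor should confirm the 12 weeks. If a stricter maintenance limit is intended, remove the 4-week wording for maintenance instead and state the stricter limit openly.

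The cost is amendment wording in Section 6 and 6.2. Sample size, visit schedule and data collection do not change.
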